At-home assessment. Participants who report symptoms of sleep apnea and attend baseline in person will be asked to wear the holter monitor/electrocardiogram (SpaceLabs Healthcare EVO device) for one night in their own homes and in their own bed to rule out diagnosis of sleep apnea. The research assistant will prepare eligible participants who screen positive for sleep apnea for this assessment using SpaceLabs Healthcare EVO devices. Monitoring will be completed in accordance with recommendations for sleep assessment (Stein & Pu, 2012). HRV monitoring will provide an index of autonomic arousal (which has been linked to sleep impairment) and an apnea hypopnea index (a measure of sleep apnea). Participants who demonstrate an apnea hypopnea index greater than 15 will be referred for polysomnography and treatment of sleep apnea.

All participants will also be asked to wear the actiwatch 24/7 and complete two full weeks of daily sleep diaries to confirm diagnosis of insomnia (>30min sleep onset latency or wake after sleep onset 3+ nights per week). Sleep diaries will be collected electronically and time-stamped each morning using the Qualtrics data management system. Participants will be asked to complete the diary each morning before noon. Those who have not completed the diary by noon will receive a reminder text or phone call from study staff.

Randomization. Participants who are eligible based on the at-home assessment will be randomized to the CBT-I or sleep hygiene only conditions.

Table 1. Assessment, therapy, and payment schedule

Week	Assmt	CBT-I	Paymt	Bonus
1	BL		30	
2		S1	20	20
3		S2		
4	Mid-tx	S3	20	
5		S4		
6	Post-tx	S5	20	
7		(S6)	30	30
8				
9				
10				
11				
12				
13				
14				
15				
16				
17				
18				
19				
20	3mo		50	
21			40	40

Note. 1mo = 1-month. Assmt = assessment. BL = baseline. Bonus = bonus payment (for completion of all previous 14 days of sleep diaries). Paymt = standard payment. Tx = treatment.

Return baseline assessment visit. Participants will be informed of their condition following the two weeks of at-home assessment. During their return visit, one of the research assistants will also provide all participants with a one-page handout on sleep hygiene, which will include personalized normative feedback on their alcohol use. The research assistant will walk the participant through the sleep hygiene handout and answer any questions they may have about the information.

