Cognitive Behavioral Therapy for Insomnia (CBT-I). Participants assigned to the CBT-I condition will attend 1-hour individual sessions of CBT-I once a week for five weeks. A sixth week of treatment will be included – and scheduled for the same date as the post-treatment assessment – if the participant and research team agree that it would be beneficial (e.g., if a participant has difficulty grasping cognitive therapy concepts). Zoom video service will be utilized for remote appointments when necessary. Consistent with clinical guidelines (Schutte-Rodin, Broch, Buysse, Dorsey, & Sateia, 2008), treatment will include stimulus control (e.g., limit use of bed to sleep or sexual activity, get out of bed if lying awake for more than 20 minutes), sleep restriction (limit time in bed to amount of time spent sleeping on a typical night), sleep hygiene (e.g., avoid exercise within 2 hours of bedtime, create cool and dark sleep environment), relaxation training, and cognitive restructuring. All patient interactions will be conducted under the weekly supervision of [name], a licensed clinical psychologist who specializes in addiction treatment. In turn, [name] will be supervised by [name], a licensed clinical psychologist who is board certified in behavioral sleep medicine.

Sleep hygiene. All participants will receive a one-page handout on sleep hygiene that includes personalized normative feedback on their alcohol use. This is the only intervention that participants assigned to the Sleep Hygiene condition will receive and is consistent with what may be expected as standard care in a doctor's visit with a primary care physician. A sleep coach will then call to check in on sleep hygiene participants' progress each week for five weeks. We did not include a control condition that was matched with CBT-I for time and content, given our focus on preliminary outcomes.

Personalized normative feedback on alcohol use. As part of the sleep hygiene recommendations, participants will receive personalized normative feedback on their alcohol use. Normative feedback will be modeled after previously utilized, efficacious interventions (Pedersen, Parast, Marshall, Schell, & Neighbors, 2017). Feedback will portray a bar graph and explanatory text comparing personal drinking quantity to that of same-sex peers.

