Follow-up assessments. To enhance follow-up rates, participants will receive up to \$300 for completion of all phases of this study. The proposed payment schedule is as follows:

Baseline		Up to \$70
Clinical interview (Zoom)	60-90min	\$0
Online survey	30-45min	\$30
14 days of actiwatch	---	\$20
14 consecutive diaries	2-3min/day	
-7 in a row to be eligible		needed for eligibility, \$0 bonus
-10 in a row		\$10 bonus
-14 in a row		\$20 bonus
Mid-Treatment		Up to \$20
Online survey	10-15min	\$20
Post-Treatment		Up to \$80
Online survey	30-45min	\$20
-phone only	5min	\$10
14 days of actiwatch	---	\$30
14 consecutive diaries	2-3min/day	

-7 in a row		\$10
-10 in a row		\$20
-14 in a row		\$30
3-Month Follow-Up		Up to \$130
Online survey	30-45min	\$50
-phone only	5min	\$20
14 days of actiwatch	---	\$40
14 consecutive diaries	2-3min/day	
-7 in a row		\$10
-10 in a row		\$20
-14 in a row		\$40

Participant retention. To enhance follow-up rates, participants will receive up to \$70 for completion of the baseline, \$20 for the mid-treatment assessment, up to \$80 for the post-treatment assessment, and up to \$130 for the 3-month follow-up; for a total of up to \$300. They will also receive reminder texts/calls, have access to free parking outside the research lab, receive immediate payment, and have access to after-hours ‘on-call’ support. We will also send all participants a personalized “thank you” note following study completion.

Blinding. [name] will not be blinded to block size or participant assignment because she will inform study therapists of participant assignment to conditions. However, [name] and study therapists will be blinded to assessment outcomes, and the assessment RA will be blinded to participant condition. All participants will be told that they are receiving treatment for insomnia in order to blind them to condition assignment (sleep hygiene will be described as “brief” insomnia treatment, and CBT-I will be described as the “most intense” treatment).

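### Participant blinding is claimed, but participants are told their condition under labels that rank the arms, so the self-rated sleep outcomes are not blinded

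*Combined protocol and SAP*

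**What the plan says.** Four parts of the combined protocol and SAP bear on this.

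- **Section 4, Blinding.** The plan claims a participant blind: "All participants will be told that they are receiving treatment for insomnia in order to blind them to condition assignment". The explanation in brackets is that "sleep hygiene will be described as “brief” insomnia treatment, and CBT-I will be described as the “most intense” treatment". The paragraph adds that "the assessment RA will be blinded to participant condition".
- **Section 4, Return baseline assessment visit.** "Participants will be informed of their condition following the two weeks of at-home assessment".
- **Section 4, descriptions of the two conditions.** CBT-I participants "will attend 1-hour individual sessions of CBT-I once a week for five weeks", with an optional sixth session. Controls receive a single-page handout, after which: "A sleep coach will then call to check in on sleep hygiene participants' progress each week for five weeks". The protocol discloses the imbalance: "We did not include a control condition that was matched with CBT-I for time and content, given our focus on preliminary outcomes". Both arms receive the same personalised feedback on drinking.
- **Section 7a, Primary Outcomes.** The list contains satisfaction (Client Satisfaction Questionnaire), drinking (Timeline Followback, TLFB), alcohol consequences (BYAACQ), the ISI and the daily sleep diary, all reported by the participant. It also contains actigraphy, which is to be combined with self-report, and recruitment and retention, both defined by attendance at CBT-I sessions.

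**The concern.** A participant cannot be both blinded to condition and informed of it. If the claim stands, readers of the eventual report will credit the trial with protection that it does not have.

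The protection matters most where the participant is the measuring instrument. The ISI asks about satisfaction with sleep, worry and distress, and the diary asks for estimated wake times and a sleep-quality rating. Someone told that they have the most intense of the treatments may report more improvement than someone told that theirs is brief, whatever happened to their sleep. Keeping the research assistant unaware of the condition does not touch that route. Section 8 plans between-group Cohen's d with 95% confidence intervals, so a difference in reporting would pass straight into the estimates meant to inform later work.

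**Working it through.** **1. Can the two statements be reconciled?**

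| Place | What the participant knows |
|---|---|
| Section 4, Blinding | Said not to know the condition; told that it is an insomnia treatment |
| Same sentence | Told that it is the brief one or the most intense one |
| Section 4, Return baseline assessment visit | Told the condition after two weeks at home |
| Section 4, condition descriptions | Receives weekly one-hour sessions, or a handout with weekly calls |

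The mildest reading is that participants learn a label but not which arm is the control. It does not rescue the claim, because the labels themselves order the arms by intensity and the contact received confirms the order. Randomisation and disclosure follow the baseline diary and actigraphy period, so the mid-treatment, post-treatment and 3-month outcomes all come after disclosure.

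**2. Which outcomes are exposed?**

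- ISI and diary: participant-rated, on the subject that the script addresses. Exposed.
- Satisfaction: participant-rated, and about the treatment itself. Exposed.
- TLFB and BYAACQ: participant-rated, but the script concerns insomnia and both arms get the same alcohol feedback. Possible, not shown.
- Actigraphy: not a self-rating, so less exposed, but only if analysed apart from self-report.
- Recruitment and retention: defined in the CBT-I arm only, so there is no between-arm contrast to bias.

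**3. Is there a figure to reproduce?**

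The blinding statement contains none. The sample size in Section 8 does reproduce. With f = .25, N = 44, m = 4 repetitions and ρ = .40, λ = f²Nm/(1 − ρ) = 0.0625 × 44 × 4 / 0.60 = 18.33 on 3 and (44 − 2) × 3 = 126 degrees of freedom, and power is .957. Inflating for 35% attrition, 44/0.65 = 67.7, hence 68. Nothing in this depends on blinding, so no sample size changes.

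**4. Illustration of consequence (assumed bias).**

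Take a two-sample t-test at one time point, n = 22 per arm (Abstract), two-sided α = .05, 42 degrees of freedom and no true effect. A between-arm reporting bias of d gives a noncentrality of d√(n/2) = d√11.

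| Assumed d | Noncentrality | Rejection rate |
|---|---|---|
| 0 | 0 | 5.0% |
| 0.1 | 0.33 | 6.2% |
| 0.2 | 0.66 | 9.9% |
| 0.3 | 0.99 | 16.3% |
| 0.4 | 1.33 | 25.4% |
| 0.5 | 1.66 | 36.7% |

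The values of d are assumptions; the documents supply none. The planned analysis is a multilevel model, so the table shows only how quickly a modest bias would matter at this sample size.

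**The case against.** The strongest reply is that participants in a behavioural trial can rarely be blinded. The plan openly says that the control is unmatched and efficacy preliminary, and the difference in contact would be obvious under any wording. That is right as far as it goes. Neutral labels would leave most of the visible asymmetry in place, and the labels' own share cannot be isolated. It does not defend the statement that participants are blinded.

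Four stronger readings are tempting, and the documents do not support them.

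- **That nearly every efficacy outcome is biased.** Recruitment advertises insomnia treatment, the script is about insomnia, and the alcohol feedback is common to both arms. Nothing shows that the labels create unequal expectations about drinking.
- **That the bias cannot be separated from a treatment effect.** Actigraphy is already a Section 7a measure, with 14 days scheduled at baseline, post-treatment and 3 months. For sleep, a less expectancy-prone comparison is within reach; what is missing is a stated role for it.
- **That the script certainly lowers expectancy among controls.** They are told that they are receiving insomnia treatment, not that they are controls, which may raise it. The net direction is an inference.
- **That the bias is a known share of the effect.** Section 3 gives between-group effects of 0.5 to 0.8, but no document gives a numerator. An assumed 0.1 to 0.3 SD yields anything from 0.1/0.8 = 12.5% to 0.3/0.5 = 60%, which is no finding.

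The consent pages and a stretch of the later text are not available, so the full script, and any expectancy item in it, cannot be checked.

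**Conclusion.** The contradiction is certain: the plan states a participant blind that its own procedures remove before any post-baseline outcome. The trial is at most assessor-blinded, and that gives little protection to the ISI and diary. It is plausible that expectancy favours CBT-I on those outcomes, but this is inferred from the ranked labels and the unequal contact; part of it comes from the contact, which the protocol discloses. Its size is unknown. Alcohol outcomes should not be described as biased on this evidence. The point should be corrected, but it does not undermine the design.

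**What to change.** 1. Reconcile the Blinding and Return baseline assessment visit paragraphs. Delete the participant-blinding claim and describe the trial as assessor-blinded only. This is a text change and serves all participants.
2. Name one stand-alone actigraphy outcome before analysis, and analyse it separately from self-report as the objective check on the self-reported sleep effect. Wake after sleep onset or total sleep time are candidates, since Section 7a claims validity against polysomnography for both. State whether diary entries enter the scoring. Qualify conclusions from the ISI and diary accordingly. The data are already being collected, including from remote participants who agree to return the device. The limits are that actigraphy is not scheduled at mid-treatment and says nothing about drinking.
3. For remaining enrolees, describe the arms in words that do not rank them, and record which script each participant heard. This needs ethics approval and creates two script periods. The reach may be small. The protocol is version 13 of December 2022, and existing participants were to be contacted by March/April 2021, so at least about 20 months of a planned 34 had passed.
4. If an expectancy item is added, place it just after condition disclosure. At mid-treatment, after three sessions, it would mix expectancy with early response.

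Items 1 and 2 are the dependable core; items 3 and 4 help only those still to enrol.

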- (2) To evaluate the effect of insomnia treatment on insomnia severity, total wake time, and sleep quality.
- (3) To evaluate preliminary treatment efficacy in reducing alcohol use, alcohol-related problems, and proposed mediators.

3. Background

Three out of four returning Veterans report heavy drinking in the context of poor sleep health (Swinkels, Ulmer, Beckham, Buse, & Calhoun, 2013). **The co-occurrence of these behaviors**, in combination with the anticipated stigma of mental health treatment (Vogt, Fox, & Di Leone, 2014), **represents a barrier to wellness among Veterans** (CDC, 2015; Fuehrlein et al., 2016). Symptoms of insomnia have been associated with elevations in alcohol use and related problems among returning Veterans (Luxton et al., 2011; [name], DiBello, Carey, & Pedersen, 2017; Swinkels et al., 2013). While the precise mechanisms underlying these associations are unclear, we propose four distinct pathways. First, insomnia has been associated with (1) deficits in executive functioning (Alhola & Polo-Kantola, 2007; Benitez & Gunstad, 2012; Fortier-Brochu & Morin, 2014), which may lead to poor decision-making and increased risk of alcohol problems (Day, Kahler, Ahern, & Clark, 2015). Insomnia symptoms have also been associated with (2) negative emotionality (Pickett, Barbaro, & Mello, 2015; Sandru & Voinescu, 2014), which may exacerbate alcohol problems in the context of heavy drinking (Watkins,

Franz, DiLillo, Gratz, & Messman-Moore, 2015), and (3) greater craving for alcohol (Mason, Light, Williams, & Drobis, 2009), which is a predictor of alcohol use (Bujarski & Ray, 2014). (4) Finally, insomnia may lead to use of alcohol as a sedative (Brower, Aldrich, Robinson, Zucker, & Greden, 2001).

[figure not shown]

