Treatment integrity. Treatment integrity will be assured in three steps. (1) Delivery. The study therapist will receive training in use of the treatment manual via audio-recorded mock therapy sessions. [name] and co-I [name], both of whom are licensed clinical psychologists, will evaluate audiotapes of mock sessions and provide corrective feedback. All intervention sessions will be audio-recorded, given participant permission. [name] and [name], who is board certified in behavioral sleep medicine, will review session audiotapes for ongoing training and supervision. [name] will score five randomly selected tapes to assess treatment fidelity using a checklist of treatment elements. Descriptive analyses will be used to determine the proportion of intended treatment elements covered in intervention sessions. (2) Comprehension. Participants will be provided with a workbook detailing treatment instructions, rationale, and handouts and encouraged to ask questions. (3) Enactment. Workbooks will contain written instructions on home assignments, and therapists will encourage assignment completion.

Early termination. All participants will receive sleep hygiene recommendations and personalized feedback on their alcohol use immediately following baseline assessment, so every participant who attends baseline will receive some form of treatment for insomnia and heavy drinking. However, participants may decide to stop participating in the study at any time without penalty. If they decide to withdraw their participation, therapy will be terminated. This will be discussed as part of the informed consent process.

5. Inclusion/Exclusion Criteria

Eligible participants will (a) be OEF/OIF/OND-era Veterans, defined as military service after September 11, 2001; (b) report either 1+ heavy drinking episode, defined as 4/5+ drinks for women/men, or 1+ alcohol-related consequence in the past 30 days; and (c) meet DSM-5 and research diagnostic criteria for Insomnia Disorder. Criteria for insomnia include difficulty (>30min) falling asleep, staying asleep, or waking up too early on 3+ nights per week for 3+ months that occurs despite adequate opportunity and circumstances for sleep and results in daytime impairment (impairment operationalized as Insomnia Severity Index scores ≥ 10).

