Insomnia Severity Index. The Insomnia Severity Index (Morin, Belleville, Belanger, & Ivers, 2011) will be used as a 7-item measure of insomnia severity in the past two weeks. Items assess difficulty falling or staying asleep, satisfaction with current sleep pattern, interference with daily functioning, the extent to which others notice their sleep problems, and worry/distress related to sleep problems. Response options range from 0 (not at all worried) to 4 (very much worried), with possible total scores ranging from 0 to 28. Participants scoring 10 or higher will be classified as screening positive for insomnia (Morin et al., 2011). Notably, self-report is the recommended method of assessment for symptoms of insomnia in adults (Schutte-Rodin et al., 2008).

Actiwatch 2. The Actiwatch 2 (Philips Respironics) is a watch-like device that monitors body movement. Actigraphy data will be used in conjunction with self-report data to estimate sleep onset latency, wake after sleep onset, and total sleep time. Data will be analyzed by proprietary software using 30s epochs. Actigraphy provides valid estimates of nighttime awakenings, wake after sleep onset, total sleep time, and sleep efficiency when compared to polysomnography (Kushida et al., 2001; Lichstein et al., 2006).

Daily Sleep Diary. The sleep diary used in this study includes all elements of the consensus sleep diary used in sleep studies across the nation (Carney et al., 2012). Participants will estimate what time they got into bed, what time they tried to go to sleep (bedtime), how long it took them to fall asleep (sleep onset latency), the total duration of nighttime awakenings (wake after sleep onset), the time of their final awakening (waketime), and what time they got out of bed for the day. Sleep onset latency and wake after sleep onset will be summed to

estimate total wake time. Total wake time will be subtracted from time in bed to estimate total sleep time. Participants will also rate sleep quality on a scale from 0 (very poor) to 4 (very good). Finally, they will be asked to report the number of standard drinks consumed; if they used alcohol (yes/no), marijuana (yes/no), or other illicit drugs (yes/no) to help with sleep; and the name, dose, and time of any sleep medication they used to help with sleep.

7b. Secondary Outcomes

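### Diary total wake time, an Objective 2 outcome, leaves out time awake in bed after the final awakening, so any CBT-I effect on that interval is invisible in it

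*Combined protocol and SAP*

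**What the plan says.** Objective 2 (Section 2) is "To evaluate the effect of insomnia treatment on insomnia severity, total wake time, and sleep quality". Total wake time is thus a named outcome, and its diary measure is listed under Section 7a, Primary Outcomes.

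The Daily Sleep Diary paragraph of Section 7a gives the derivation: "Sleep onset latency and wake after sleep onset will be summed to" estimate total wake time. The same paragraph lists the diary items "the total duration of nighttime awakenings (wake after sleep onset), the time of their final awakening (waketime), and what time they got out of bed". Wake after sleep onset therefore means awakenings during the night, and the final awakening and rising time are separate items. The paragraph then says: "Total wake time will be subtracted from time in bed to estimate total sleep time". It does not say when time in bed starts or ends.

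Section 5 defines the insomnia complaint as "difficulty (>30min) falling asleep, staying asleep, or waking up too early on 3+ nights per week for 3+ months". Section 4 describes a CBT-I package that includes stimulus control (leaving bed when lying awake) and "sleep restriction (limit time in bed to amount of time spent sleeping on a typical night").

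The Actiwatch variables in Section 7a are latency, wake after onset and total sleep time. None of them isolates wake after the final awakening.

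**The concern.** The outcome carries the name total wake time but covers only two of the periods in which a participant can lie awake. The third, from final awakening to rising, is where early waking shows itself, and the protocol treats early waking as a core symptom. Two CBT-I components bear on time spent awake in bed, whereas the control arm receives a handout and check-in calls. A between-arm difference in this interval is therefore plausible, and the defined outcome cannot show it.

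There is a second consequence. Subtracting an incomplete wake time from time in bed may count the missing minutes as sleep. Redefining the window for total sleep time would repair that variable only; total wake time would still be latency plus wake after onset.

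**Working it through.** **The plan's own figures.** Section 8 gives N = 260, 44 and 18 for f = .10, .25 and .40 (alpha .05, power .95, 2 groups, 4 repetitions, correlation .40). Using a noncentral F with lambda = f² × N × 4 / (1 − .40), df1 = 3 and df2 = 3(N − 2), these reproduce, with power .951, .957 and .956. Recruitment is 44 / .65 = 67.7, rounded up to 68. None of this is disputed. N was set on generic effect sizes, not on total wake time, so the point does not change it.

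**One night under the definitions (assumed values).** Tries to sleep 23:00, latency 35 min, wake after onset 20 min, final awakening 04:30, out of bed 06:30.

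- Total wake time as planned: 35 + 20 = 55 min.
- Final awakening to rising: 04:30 to 06:30 = 120 min.
- Wake including that interval: 55 + 120 = 175 min.
- Window 23:00 to 06:30 = 450 min. Total sleep time as planned: 450 − 55 = 395 min. With full wake time: 450 − 175 = 275 min.
- Check: 23:00 to 04:30 is 330 min, less 55 awake, which is 275 min asleep.

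With this window, each minute awake after the final awakening adds nothing to total wake time and one minute to total sleep time.

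**What inclusion would do to a between-arm comparison.** The documents give no mean, SD or expected change for either quantity, so every input here is an assumption: effect on latency plus wake after onset 30 min, SD 45; added effect e on wake after the final awakening, SD s; correlation r between the two; 22 per arm; two-sided two-sample t-test at .05.

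Current sum: d = 30/45 = .67, power .58.

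Extended sum: d = (30 + e) / √(45² + s² + 2 × r × 45 × s).

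| s | r | SD of sum | d at e = 0 | d at e = 10 | d at e = 20 | Break-even e |
|---|---|---|---|---|---|---|
| 25 | 0 | 51.5 | .58 | .78 | .97 | 4.3 |
| 25 | .3 | 57.7 | .52 | .69 | .87 | 8.4 |
| 40 | 0 | 60.2 | .50 | .66 | .83 | 10.1 |
| 40 | .3 | 68.6 | .44 | .58 | .73 | 15.7 |

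Break-even solves (30 + e)/SD = 30/45, so e = (2/3) × SD − 30; for example (2/3) × 51.48 − 30 = 4.3.

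With s = 25, e of 10 to 20 min gives d of .69 to .97 and power of .61 to .88. The share of the raw reduction not captured by the current sum is then 10/40 = 25% to 20/50 = 40%. With e = 0 the share is 0% and d falls to .52 to .58. With e = 5 and r = .3, d is .61 and power .50, below the current definition.

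**The case against.** A reader might infer that the Objective 2 estimate is too small and that the trial loses power through this definition. The documents do not support that. It holds only if CBT-I shortens wake after the final awakening, and nothing in them gives the size of such a change. As the table shows, a small added effect with realistic extra variance lowers d. The t-test is also a simplification, since Section 8 plans multilevel models. This part of the objection stands.

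Latency plus wake after onset is a legitimate measure in its own right, and the at-home assessment in Section 4 confirms insomnia on those two components only. Enrolled participants are thus selected on what the current sum counts, and two hours awake before rising is an illustration, not a typical night. That also stands. It does not remove early waking that accompanies onset or maintenance problems, and it does not make the sum total.

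The added term is partly behavioural. In the example, someone who still wakes at 04:30 but rises at 04:50 would score 35 + 20 + 20 = 75 min instead of 175, a 100-min drop with no extra sleep. The term would also count voluntary lying in. This is a real cost, and it is why the components need to be shown separately.

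Extending total wake time without fixing the time-in-bed window can create a new error. If the window ended at the final awakening, total sleep time would become 330 − 175 = 155 min instead of 275, too low by 120. The two definitions must change together.

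Finally, this is version 13, dated 12/29/2022, and Section 8 has monitoring board reports that include interim analyses. A change to a named outcome at this stage needs a documented date and a reason that does not rest on a hoped-for larger effect.

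**Conclusion.** The definitional point holds on the text alone. Section 7a excludes wake after the final awakening from the outcome called total wake time, and no other section counts it. The consequence for total sleep time is conditional: it arises if time in bed runs to the out-of-bed time, which the plan leaves undefined.

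Any CBT-I effect on the omitted interval is invisible in this outcome. Its size, and the direction in which inclusion would move the standardized effect and power, cannot be determined from the documents. Under the assumed 30-min effect and SDs of 45 and 25 min, d rises only if the added effect exceeds about 4 to 8 min; with an SD of 40 for the added term, the threshold is about 10 to 16 min. The reason to change the definition is that the variable should measure what its name and the objective state. A power gain is not an established reason. The planned sample size is unaffected.

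**What to change.** In Section 7a, Daily Sleep Diary:

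1. Define total wake time as sleep onset latency + wake after sleep onset + (time out of bed − time of final awakening).
2. State that time in bed, for the total sleep time calculation, runs from the time of trying to sleep to the time out of bed, and that total sleep time is this window minus the redefined total wake time. Time between getting into bed and trying to sleep then falls outside both variables.
3. Report latency plus wake after onset, and wake after the final awakening, as separate components by arm.
4. Record the change and its date before outcome analysis.

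The cost is a few lines of text and a changed derivation. The diary already collects "the time of their final awakening (waketime), and what time they got out of bed for the day", so no new data or participant burden is needed and existing records can be re-derived. The downside is that the added term brings variance and partly reflects adherence to the instruction to leave bed when awake. The separate components let a reader see how much of any difference comes from that term.
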